medicine. We have successfully developed the software for our clinicians to perform point of care randomization without interrupting patient care. Patient-Centered Outcomes Research Institute (PCORI) recently awarded our center ([name]) an award for a multi-state study on “comparative effectiveness of pain cognitive behavioral therapy and chronic pain self-management within the context of opioid reduction”. We are using CHOIR and the same point of care randomization tool for this study of over 1000 patients (<https://www.pcori.org/research-results/2017/comparative-effectiveness-pain-cognitive-behavioral-therapy-and-chronic-pain>). Similarly, American Society of Anesthesiologists Foundation for Anesthesia Education and Research awarded the principal investigator for another study using CHOIR for point-of-care randomization (comparative effectiveness of duloxetine and desipramine in patients with chronic pain).

(c) Approach:

Study Design: We are proposing to conduct a pragmatic randomized clinical trial to compare long-term effectiveness of two novel spinal cord stimulation waveforms: high frequency and burst. We are planning to study the superiority of high frequency spinal cord stimulation in improving pain and function, and superiority of burst spinal cord stimulation in improving depression and anxiety.

Patients: We will enroll chronic pain patients referring to Stanford Pain Management Center who meet the following inclusion and exclusion criteria:

Inclusion Criteria:

1. Adult English-speaking patient 18 years old or above
2. Persistent pain in lower back and/or leg for more than six months
3. Candidate for spinal cord stimulation (with either high frequency or burst waveforms) based on recommendations from Stanford Pain Management Center Neuromodulation Multidisciplinary Team Conference.

Exclusion Criteria:

1. Motor weakness in neurological examination in lower body based on the assessment by treating pain physicians
2. Previous failed spinal cord stimulation trial with either high frequency or burst waveforms
3. Patient refusal

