appropriate skin preparation and draping, fluoroscopy will be used to identify and mark vertebral body levels from T8 to L2. After infiltrating skin and subcutaneous tissue with local anesthetic for analgesia, we will access epidural space at most convenient lumbar space using a 14-gauge Tuohy needle. Epidural access will be confirmed using loss of resistance technique to air with a pulsator syringe. We will then insert an 8-contact, styletted trial lead through the needle. We will advance the lead through posterior epidural space at midline using live fluoroscopy imaging. We will place the tip of the lead at the superior border of T8 vertebral body. We will then access the epidural space and insert a second lead in a similar fashion. The tip of the second lead will be in the middle of T9 vertebral body; the contacts will be staggered with the other lead. We will then check the impedance of the contacts. After confirming appropriate placement, we will remove the needles and lead stylets under live fluoroscopy imaging. We will secure the leads and apply transparent occlusive dressing. We will then transport the patient to post-anesthesia care unit. A representative from the manufacturer will connect the leads to an external pulse generator which will be secured in a small bag around patients' waist. The manufacturer representative will then program the device and will be communicating with the patient daily during the trial period. The trial period will be 5-10 days. We will instruct the patients to maintain the same routine and even try to be more active to test efficacy of the treatment. We will also instruct the patients to keep the dressing, the leads and external pulse generator completely dry. The external pulse generator will deliver the therapy continuously during the trial period. High frequency waveform will be delivered with following parameters: frequency of 10,000 hertz, pulse width of 20 microseconds, and amplitude of 0-15 milliamperes. The patients will return to our clinic at the end of the trial period to remove the trial leads and discuss the treatment outcome. If the patients report more than 50% pain relief and/or improvement in function, they will be scheduled for implant of permanent spinal cord stimulation system at least two weeks after removal of trial leads.

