The trial and implant process will be identical to high frequency with one difference: correct placement of the leads will be confirmed during the trial procedure by inducing paresthesia over the painful area (instead of standard anatomical placement with high frequency). The parameters of the stimulation are as below: each burst includes 5 pulses of electrical stimulation at intra-burst frequency of 500 hertz without time for discharge in between pulses. These bursts will be repeated at inter-burst frequency of 40-60 hertz. The amplitude will range between 0 and 15 milliamperes.

Data Collection: As a part of evaluation for spinal cord stimulation, patients in our clinic complete initial survey on Collaborative Health Outcomes Information Registry (CHOIR). The participants will receive electronic surveys via email at 1, 3, 6, 12, 18, 24 and 36 months after the operation for implant of spinal cord stimulator (or trial in case of failed trial). The participants will receive email reminders after three and five days if the surveys are not completed. If the participants do not complete the surveys within seven days of receipt of the survey link, they will be contacted to be reminded of the survey. These surveys will include average and worst Numerical Rating Scale (NRS) of pain; National Institute of Health (NIH) Patient Reported Outcomes Measurement Information System (PROMIS) measures for function, pain interference, depression and anxiety; patient global impression of change on a 7-point Likert scale; and questions about any adverse events related or unrelated to the therapy. Data about use of other analgesics and medications, and pain interventions

will also be recorded at these intervals from participants' electronic health records and California Prescription Drug Monitoring Program. We will also record participants' baseline characteristics including age, sex, main pain diagnosis, other pain diagnoses, psychological comorbidities, medical comorbidities, medication use, and education level.

Adverse events will be reported to the principal investigator either directly by the participants or through the treating pain physician at Stanford Pain management Center. The principal investigator is responsible for reporting the adverse events and deviations from the protocol appropriately to institutional review board and other authorities.

Mood instability will be monitored as a component of routine clinical care by treating physician.

Outcomes:

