We will use SAS Enterprise Guide (SAS Institute Inc., Cary, NC) for all analyses. Our null hypotheses are similarity of measures. We will perform a two-sided hypothesis testing with accepted type I error of 0.05. We will compare baseline characteristics using t-test for continuous variables and chi-square for categorical variables. We will adjust for the variables that are different between the groups in our final regression model. Our primary analysis will be based on modified intention-to-treat. We will only exclude patients with no follow up data from our final analysis. We will then perform a secondary analysis based on implants only (excluding patients who do not achieve appropriate pain control in trial period).

We will then perform the following subgroup analyses:

1. Patients who have undergone lumbar spine fusion versus patients who have not.
2. Patients with back pain only (based on baseline body map) versus patients with back and leg pain or leg pain only.

3. Patients with PROMIS depression measure of above 90th percentile in baseline evaluation.
4. Patients with PROMIS anxiety measure of above 90th percentile in baseline evaluation.

The rate of CHOIR survey completion is more than 60% in our routine clinical care. We expect a higher rate for our proposed study considering that these surveys are abbreviated, and participants will receive more frequent reminders as well as telephone reminders (currently patients receive only one email reminder to complete the survey). For our primary outcome we will try to minimize missing data by calling the patients who do not complete the surveys up to seven times; we will try to ask and record the pain intensity even if they are not willing to complete surveys. Our analysis model will allow for missing data in longitudinal variables, subject to assumption of missing at random.

Data and Safety Monitoring Plan: We will not perform any interim analyses for benefit, harm or futility. We will establish a data and safety monitoring board consisting of investigators, at least two independent clinicians in our clinic (not part of the study team), and at least one neurosurgeon subspecialized in spine surgery who will monitor the study quarterly for adverse events and patient safety, reporting of adverse events, enrollment pace and study timeline, quality of data, and deviations from the protocol.

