Sample size: The highest standard deviation of NRS pain scale in our clinic is 2.25 based on prior publications.^{19,21-25} Accepting type I error of 0.05 with 80% power, we will require 80 participants per group to detect one unit between-group difference in change from baseline in NRS pain scale. We are proposing a more conservative (larger) sample size to preserve power considering that some patients do not proceed from trial to implant and do not receive therapy. Currently more than 80% of patients who undergo a trial of spinal cord stimulation proceed to receiving an implant. We will therefore target 100 patients in each arm. Correlation between repeated measure will decrease variance and increase the power of the proposed study.

Timeline: Stanford Pain Management Center performed more than 120 trial of spinal cord stimulation in 2017 and this practice is increasing in our division. We expect a high consent rate considering the nature of our study. We believe we will be able to complete recruitment in two years; thus, last follow up of last recruited patient will be completed by five years.

Data Management: CHOIR will be the main tool for data collection and storage for the study. At completion of the study, the data from CHOIR, participants' electronic health records and California Prescription Drug Monitoring Program will be downloaded for analysis. After initial steps of data preparation, we will de-identify the dataset for further analysis. The principal investigator will save the de-identification code on a secure computer within Stanford University Network only.

Limitations:

1. One of the most important advantages of pragmatic clinical trial with less stringent inclusion/exclusion criteria is to improve the ability to generalize the results to a wider range of patients. However, considering that the current study is a single center study conducted in a tertiary pain management center, our sample might not be representative of chronic pain patients seen by community pain providers.
2. Our aim is to integrate our trial into patient care; thus, we are not blinding the provider and the participants. Method of data collection is similar in both groups and does not involve interaction with investigators. This will minimize, but not eliminate, the bias introduced by proceeding with an open label design.

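### Follow-up surveys are timed only from implant or a failed device trial, so a randomised patient who has neither gets no scheduled survey and can leave the modified intention-to-treat set

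*Combined protocol and SAP*

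**What the plan says.** **Order of events.** Under Randomization, the treating physician randomises the patient at a clinic visit. The High Frequency and Burst sections both place scheduling of the device trial after that. Under High Frequency, patients who respond to the trial proceed as follows: "they will be scheduled for implant of permanent spinal cord stimulation system at least two weeks after removal of trial leads". The Burst section adopts the same process apart from how lead placement is confirmed.

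**Survey clock.** Data Collection sets seven surveys, the first at month 1 and the last at month 36, with the time counted in "months after the operation for implant of spinal cord stimulator (or trial in case of failed trial". Specific Aims names implant as the only origin. The primary outcome, change in pain at 12 months, has no origin of its own. Medication and intervention data from records "will also be recorded at these intervals from" the health record and the state prescription database, so they use the same clock.

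**Chasing missing data.** Email reminders and a follow-up contact are triggered by an uncompleted survey. For the primary outcome, the Analytic Plan adds "calling the patients who do not complete the surveys up to seven times".

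**Analysis sets.** The primary analysis is modified intention-to-treat: "We will only exclude patients with no follow up data from our final analysis". There is also a "secondary analysis based on implants only (excluding patients who do not achieve appropriate pain control in trial period".

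**The concern.** The clause on failed trials shows that the sponsor meant to follow patients who are not implanted. It covers only one way of not being implanted. A patient may also be randomised and never reach the device trial, or pass the trial and not go on to implant. Neither has a stated survey origin. If they contribute no outcome data, it is because the schedule never asked them, not because they refused or failed to respond.

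The plan then treats the absence of follow-up data as grounds for exclusion from the primary analysis. The repeated-measures model, which assumes data are missing at random, does not help here, because an excluded patient contributes no follow-up outcome to it. Allocation is open and the two devices come from competing manufacturers, so equal attrition before the procedure is plausible but cannot be taken for granted.

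**Working it through.** **1. The routes a randomised patient can take.**

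| Route after randomisation | Survey origin in Data Collection | 12-month value defined? | Reached by reminders and calls? |
|---|---|---|---|
| Trialled, implanted | Implant date | Yes | Yes |
| Trialled, trial failed | Trial date | Yes | Yes |
| Trialled and passed, not implanted | None, unless a failed trial is read broadly | Not on the plain reading | Not on the plain reading |
| Never trialled | None | No | No |

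The last row has no alternative reading. The third depends on what counts as a failed trial. The implants-only analysis does not settle it, since it describes the patients it leaves out only as lacking adequate pain control in the trial period.

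**2. The plan's own sample size.** Inputs from Sample size: SD 2.25, difference 1 NRS unit, two-sided alpha 0.05, power 80%. n = 2 × (1.960 + 0.842)² × 2.25² / 1² = 79.5, so 80 per group, which reproduces the stated figure. Allowing for 20% not implanted, 80 / 0.80 = 100 per arm, which reproduces the target.

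**3. Does that allowance cover the gap?** The basis for it is "Currently more than 80% of patients who undergo a trial of spinal cord stimulation proceed to receiving an implant". The denominator is patients who undergo a device trial. The figure does not count patients never trialled, and it does not divide those not implanted into failed and passed. The allowance also protects power, not comparability of the arms.

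**4. Power is not the main issue.** If the same share of each arm is lost through the gap, power for a 1-unit difference (normal approximation, SD 2.25) is 88.2% with 100 per arm, 86.5% with 95, 84.6% with 90 and 80.3% with 80.

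**5. Selection.** Let p be the share of an arm excluded and d the gap in mean 12-month change between retained and excluded patients. The retained mean differs from the full-arm mean by p × d. With the same d in both arms, the bias in the between-arm difference is (p1 − p2) × d. If d differs by arm, it is p1 × d1 − p2 × d2. Equal shares with equal gaps give zero.

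The documents supply neither p nor d, so every share and gap below is an assumption. The last column is the rejection rate of a two-sample t-test (noncentral t, SD 2.25, two-sided 0.05) when the full-arm means are equal.

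| Excluded per 100 (assumed) | Gap d, NRS (assumed) | Bias, NRS | Rejection rate |
|---|---|---|---|
| 5 vs 2 | 1 / 2 / 3 | 0.03 / 0.06 / 0.09 | 5.1% / 5.4% / 5.9% |
| 10 vs 5 | 1 / 2 / 3 | 0.05 / 0.10 / 0.15 | 5.3% / 6.0% / 7.4% |
| 10 vs 0 | 1 / 2 / 3 | 0.10 / 0.20 / 0.30 | 6.1% / 9.3% / 15.0% |

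The 10 versus 0 row is an extreme that shows the range; nothing in the documents points to it.

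**The case against.** The strongest reply is that the gap is narrow and probably nearly balanced. The plan calls the two devices similar in risk, maintenance and supporting literature. The selection conference does not favour either waveform, and the procedures differ in one step. No count or imbalance is documented. All of this stands, and it limits what can be said about size.

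Three further replies stand in part.

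- **Broad reading of a failed trial.** It could mean any trial that did not lead to implant. That would close the gap for patients who pass but are not implanted. It cannot reach patients who never had a trial.
- **Routine CHOIR entries.** Preliminary Data says clinic patients are asked for surveys at each follow-up visit. Read literally, such an entry could keep an attending patient in the set. It would not fall at a study month or supply a defined 12-month value, and the plan does not say that it counts.
- **Meaning of the rejection rates.** They assume equal full-arm means. If excluded patients do worse because they received no stimulation, and the devices are equal, unequal shares make the full-arm means themselves differ. The retained comparison then departs from the intention-to-treat effect without being a false positive for the device contrast.

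A reader might infer that the coverage exclusion in Limitations, item 3, removes patients after randomisation. The documents do not show that. It is absent from the numbered Exclusion Criteria and its timing is not stated, but it can equally be read as a limit on enrolment.

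**Conclusion.** The concern holds. Followed as written, the plan sends no survey to a randomised patient who never has a device trial, and its analysis-set rule can then remove that patient from the primary analysis. For patients who pass the trial but are not implanted, the same conclusion depends on how a failed trial is defined.

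The size is unknown and may be small. Under the assumed 5 versus 2 or 10 versus 5 exclusions per 100, the bias is 0.03 to 0.15 NRS points, against a target difference of 1. A reader might infer that the primary comparison is biased, or its type I error inflated, by a known amount. The documents do not support that: they give no count and no evidence of imbalance, and there is no bias if shares and outcomes match between arms. What is established is an avoidable route to exclusion after randomisation. It should be closed because that is inexpensive and the plan cannot otherwise show that the route is harmless.

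**What to change.** **Data Collection.** Keep the implant or failed-trial origin wherever that date exists. Give every other randomised patient a default origin, for example the randomisation date, with the same surveys, reminders and calls, so that each has a scheduled 12-month pain score. State whether a failed trial includes a passed trial without implant.

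**Analytic Plan.** Keep every randomised patient with any post-randomisation survey in the primary set. Do not discard surveys answered before a late procedure, since that would recreate the exclusion. State in advance which survey supplies the 12-month value when a procedure comes late, and whether routine-visit CHOIR entries and record-only data count as follow-up. Report by arm the numbers never trialled, trialled but not implanted (failed and passed separately), and excluded from modified intention-to-treat.

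**Exclusion Criteria.** State whether the coverage exclusion in Limitations is applied before randomisation.

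**Cost.** A small additional survey schedule must be set up in CHOIR, which already handles enrolment, randomisation and follow-up, so no new visits are needed. The time origin will differ for these patients. Because the outcome definition takes baseline from the last completion before the trial, a survey sent under the default origin must be labelled as follow-up so that it is not also used as baseline. Patients who refuse contact will still be lost.

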Randomization: After obtaining informed consent, the patients who meet the inclusion and exclusion criteria will be 1:1 randomized to undergoing treatment with spinal cord stimulation with either high frequency or burst waveforms. Treating pain physician will randomize the patient during clinic visit using CHOIR point-of-care randomization system. Randomization algorithm will be based on computer generated numbers in random blocks of four, six and eight.

Blinding: Two different competing manufacturing companies will be providing devices that deliver these two waveforms. Interacting with the manufacturer representative for programming and device maintenance will inform the patient of the type of waveform. Therefore, blinding will be challenging, and we will not attempt to blind the patients to the treatment they are receiving. The risk profile and maintenance of these devices are similar; they are novel to the patients with similar efficacy literature. Thus, we do not expect differences in either compliance or therapy expectation secondary to lack of blinding. The figure shows the process of the study up to randomization.

Intervention: At Stanford Pain Management Center, pain physicians identify candidates for spinal cord stimulation; thereafter, they refer these patients to our pain psychologists. A multidisciplinary neuromodulation team conference – which is attended by pain physicians and pain psychologists in our division – assesses appropriateness of spinal cord stimulation for these candidates based on their pain diagnosis, spinal anatomy, history of spine surgery, medical comorbidities, psychological comorbidities, expectations, cognitive status and mood stability. The team also recommends the choice of devices appropriate for each patient who is identified as an optimized candidate. With current evidence, the team does not distinguish between high frequency and burst waveforms. The checklist of items discussed during these team conferences is provided in Appendix 1. The treating physician will then obtain informed consent and randomize the patients who are identified as optimized candidates for spinal cord stimulation by multidisciplinary neuromodulation team conference. These participants will receive treatment with either high frequency or burst spinal cord stimulation.

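### No between-arm comparison of adverse events is planned, and neither the interval health-record extraction nor the fallback call names them

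*Combined protocol and SAP*

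**What the plan says.** Section (c) Approach, Data Collection, gives two routes for adverse events. The surveys emailed at 1, 3, 6, 12, 18, 24 and 36 months include "questions about any adverse events related or unrelated to the therapy". Separately, "Adverse events will be reported to the principal investigator either directly by the participants or through the treating pain physician". No schedule, form or event list is attached to this second route.

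The same section also draws, at the survey intervals, on the health record and the state prescription database. What is to be taken from them is "Data about use of other analgesics and medications, and pain interventions". Complications, revisions and explants are not among the items named.

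The Analytic Plan describes up to seven calls to patients who have not completed their survey, introduced as a way to limit missing data on the primary outcome. For those who still decline, "we will try to ask and record the pain intensity even if they are not willing to complete surveys".

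The Outcomes section lists one primary and 11 secondary outcomes: pain, global impression of change, function, pain interference, depression, anxiety and opioid dose. The Analytic Plan adds four hypotheses, an implant-only analysis and four subgroup analyses. None uses adverse events. The Data and Safety Monitoring Plan sets up a board that looks at adverse events every quarter and rules out interim analyses for harm.

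Under Blinding the plan states: "The risk profile and maintenance of these devices are similar". It relies on this, among other things, in expecting no difference in compliance or expectation from the open-label design.

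**The concern.** This is a randomised comparison of two implanted systems from competing manufacturers, followed for 36 months. Both arms involve epidural lead placement and, after a successful trial period, implant surgery. Lead position is confirmed differently in the two arms. The Innovation section notes that existing safety and efficacy data reach 24 months, so the third year is where this trial could add most. As written, it would report pain, mood, function, global impression and opioid dose by arm, and nothing on harm. A reader choosing between the devices would have only the plan's own assertion that the risks are alike.

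If someone tabulated adverse events afterwards, the data would come from patients who knew their device and completed the survey, plus whatever participants or physicians chose to report. A patient can decline the survey, be telephoned for a pain score and have the health record opened for medications, and no step in the plan asks about a complication.

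**Working it through.** **1. Setting the text side by side**

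| Contact or source | When | Adverse events named? |
|---|---|---|
| Emailed survey | 7 scheduled times | Yes, if completed |
| Report by participant or treating physician | Unscheduled | Yes, passive |
| Health-record and prescription-database extraction | At the survey intervals | No |
| Fallback call, survey declined | Tied to the primary outcome | No, pain intensity only |
| Safety board | Quarterly | Yes, oversight; no arm comparison specified |
| Outcomes, hypotheses and analyses | 12 outcomes, 4 hypotheses | No |

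The phrase about pain interventions might catch some device procedures incidentally, but the plan does not say so. Data Management mentions downloading health-record data at study end, again without naming adverse events.

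**2. The plan's own sample size**

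Inputs from Sample size: SD 2.25, difference 1 NRS unit, two-sided α 0.05, power 80%.

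n = 2 × (1.96 + 0.8416)² × 2.25² / 1² = 2 × 7.849 × 5.0625 = 79.5, so 80 per group. Allowing for 80% proceeding to implant: 80 / 0.80 = 100 per arm. Both figures reproduce. They are driven by pain intensity alone.

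**3. What 100 per arm would give for harm**

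The documents state no event rate, so the rates here are assumptions. With the same true rate p in both arms, the 95% half-width for the risk difference is 1.96 × √(2p(1−p)/n). At p = 0.10 and n = 100: 1.96 × √(0.18/100) = 0.083.

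| Assumed rate | 100 per arm | 60 per arm |
|---|---|---|
| 5% | ±6.0 points | ±7.8 points |
| 10% | ±8.3 | ±10.7 |
| 15% | ±9.9 | ±12.8 |
| 20% | ±11.1 | ±14.3 |

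The second column illustrates relying on respondents to a single survey at the routine-care completion floor (60% of 100).

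**4. Whether similarity or a difference could be shown**

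Similarity within an assumed 10-point margin (one-sided 0.025, 80% power): n = 7.849 × 2p(1−p) / 0.10². At p = 0.10 this is 7.849 × 0.18 / 0.01 = 141.3, so 142 per arm. At 5%, 15% and 20% it is 75, 201 and 252. Only the 5% case fits within 100 per arm, and there a 10-point margin would tolerate a tripling, from 5% to 15%.

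Power to detect a difference (two-sided 0.05, pooled variance under the null): Φ{[|p₂−p₁|√n − 1.96√(2p̄(1−p̄))] / √(p₁(1−p₁)+p₂(1−p₂))}. For 10% against 20% with n = 100: (1.000 − 0.990)/0.500 = 0.02, giving 51%; with n = 60 it is 33%. For 10% against 25%: 80% and 58%.

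So the planned size supports an interval estimate and detection of large differences, but not a claim of similarity at event rates of 10% or more.

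**The case against.** The plan does not ignore safety. The treating physician can report events whatever the survey status, and at a single centre an infection or explant treated there is missed only if that route also fails. The board includes at least two clinicians from outside the study team and at least one spine neurosurgeon, and it reviews event reporting and data quality each quarter. Calls to non-completers also prompt completion of a survey that contains the adverse-event questions. All of this stands. None of it supplies a by-arm comparison or a systematic search for events.

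Four stronger readings are tempting, and the documents do not support them.

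- *Capture is survey-only.* It is not, because the physician route exists.
- *About 40% of events would be lost.* The plan says "The rate of CHOIR survey completion is more than 60% in our routine clinical care" and expects better in the trial. The complement counts unanswered forms at one time point. No recall window is stated for the adverse-event questions, so a later survey may still pick up the event.
- *Early events are missed, unequally by arm.* For implanted patients the first survey falls at least 5–10 + 14 + about 30 = 49–54 days after trial-lead placement, against about 30 days after a failed trial. That is delay, not loss, and the contrast is between trial successes and failures, not between randomised arms. There is contact in between: "The patients will return to our clinic at the end of the trial period to remove the trial leads".
- *The trial cannot test similar risk.* Survey answers could be tabulated by arm. More exactly, no comparison is planned, and incomplete capture would weaken a later one. Better capture would not turn 100 per arm into a demonstration of similarity at event rates of 10% or more.

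It is also fair to say that similar risk is a supporting premise, not a trial hypothesis, and that higher non-response after complications is plausible but undocumented.

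**Conclusion.** The point holds as a gap in planned safety reporting. Adverse events are collected and overseen, but no outcome or analysis compares them by arm. The two systematic contacts that could reduce dependence on self-report, the interval record extraction and the fallback call, do not name them. The similar-risk statement therefore stays an assertion. The share of events missed cannot be derived from the documents, nor can whether it would differ by arm.

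The primary pain analysis and its sample size are unaffected. What is lost is a by-arm estimate of harm with a half-width of about 8 points at an assumed 10% rate and 100 per arm (6 to 11 points over assumed rates of 5% to 20%), supposing complete capture and equal rates in both arms.

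**What to change.** 1. **Data Collection:** add device- and procedure-related complications to the record extraction already done at each interval, counting from trial-lead placement. Examples are infection, lead migration, revision, explant, dural puncture, new neurological deficit and unplanned hospital visit.
2. **Analytic Plan, fallback call:** add one question on adverse events and device surgery beside the pain score.
3. **Outcomes and Analytic Plan:** add a secondary safety outcome, namely the proportion of patients with at least one device- or procedure-related event, and the proportion with revision or explant, by 12 and by 36 months. Report it by randomised arm as a risk difference with 95% confidence interval. Say that this is estimation, not a test of similarity, and that patients with record data but no survey data are counted.

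The cost is a few more extraction fields, one call question and one table, with no extra patients or visits. Events treated at other institutions would still depend on self-report, and the report should say so.
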